9.1.5 Definition of measurement of vital signs

The vital signs collected will be: heart rate and arterial blood pressure.

The 12 lead ECG will be recorded first of procedure, at the discharge and at the follow up visits.

9.1.6 Definition of physical examination

The physical examination will consist of measurement of weight, height, arterial blood pressure, heart rate and a standard physical exam.

[figure not shown]
9.1.7 Definition of laboratory parameters assessed at enrolment and at up to 48 h post procedure

Laboratory test consist of complete blood count, creatinine, troponin T hs and NT-proBNP. These will be assessed at enrolment and at up to 48 h post procedure or discharge whichever comes first.

9.1.8 Definition of adverse clinical events:

The Adverse clinical events are overall and CV death, ischemic and haemorrhagic stroke, systemic or pulmonary embolization, spontaneous MI, periprocedure related complications (defined in the section 5.3) and BARC bleeding grade 2, 3, or 5 (see the definitions in Appendix 1). CEC will adjudicate these adverse clinical events.

Figure 1.

9.2 Assessments of outcomes

Assessment of primary outcome

The primary outcome is the composite of LAA patency at 45 day evaluated with CCTA or the crossover from one device to the other device based on morphological/anatomical considerations during device implantation.

Patency LAA will be estimated at CCTA by measurement of the linear attenuation coefficient (Hounsfield unit, HU) in the LAA distal to the device and comparison of contrast density to atrial chamber. LAA patency was defined with $HU \geq 100$ or $HU \geq 25\%$ of the atrium, as reported in a previous publication.¹⁵ The occurrence of LAA patency will be centrally evaluated and adjudicated by an Imaging Core Lab (ICL) composed of three imaging experts who will independently score each of the studies as positive or negative for LAA patency. In the event of inconsistent primary end point adjudication between the three readers, a consensus between all of them will be required. Adjunctive CCTA criteria of complete occlusion (as described in section 10.2) will be collected in order to validate them. A TEE evaluation of PDL presence will be performed at 45-days in order to compare the two imaging technique. The crossover is defined as the switch from the randomized device to the other device based on morphological/anatomical considerations during device implantation. It will be centrally adjudicated by CEC as justified if there will be evidence that the randomly allocated device has been positioned at least once in the LAA but LAA ostium sealing remained suboptimal (peri-device leak ≥ 3 mm) or concerns were present over the device stability and consequent risk of device embolization.

Assessment of secondary outcomes

Secondary outcomes will be collected at 45 days, 6 months, 13 months, 2 years, 3 years, 4 years and 5 years follow up. Data about adverse clinical events (listed in the section 9.1.8) will be collected by means of electronic forms and related documents (medical reports, CT and other imaging report). LAA patency on arterial phase has been already defined in the previous section ("Assessment of primary outcome"). LAA patency on venous phase is defined, as reported in a previous publication,²² as a LAA density ≥ 100 HU or $\geq 150\%$ of that measured at the same site on arterial phase. Leak at TEE is defined as any communication jet between LA and LAA detectable by means of color-Doppler (high velocity 50-60 cm/sec). The size is measured taking the narrowest flow region of the jet that occurs at, or just close to, the device). Of note, rate of LAA patency at 45 day CCTA will be compared with rate of leak at 45 day TEE.

Assessment of safety outcomes

Safety outcomes will be assessed 45 days, 6 months, 13 months, 2 years, 3 years, 4 years and 5 years follow up. Data about adverse clinical events (listed in the section 9.1.8) will be collected by means of electronic forms (ICE-Advice Pharma) and related documents (medical reports, CT and other imaging report).

Assessments in participants who prematurely stop the study

Data of withdrawn participants will be collected up to the time of withdrawn. However, withdrawn participants will be asked the permission to continue collecting and evaluate data about them from routine data or other sources (general practitioners, Health System Softwares available) in order to respect the patient choice without affecting the scientific quality of the study.

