4.3 Secondary Objectives

Other secondary objectives will include the incidence of adverse clinical events in the two groups, a comparison between the two devices in terms of procedure feasibility, LAA patency and device thrombus over time as assessed with both 45-day and 13-month CCTA and with 45 day TEE. Furthermore, a secondary objective of the study will be the comparison between TEE and CCTA with respect to LAA patency and device thrombus.

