5.4 Other Outcomes of Interest

A comparison between CCTA and TEE at 45 days and then at 13 months will be performed in order to obtain a validation of CCTA to reveal the LAA patency.

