12.4 Planned Analyses

Datasets to be analysed, analysis populations

The main analysis of the primary endpoint will be conducted on all randomized patients who have completed the 45-day follow-up according to the intention to treat principle, in keeping with the superiority prespecified study hypothesis. Additional analyses of the primary endpoint will be also carried out in the per-protocol and as-treated populations. Similarly, LAA patency and DRT at 45-day and 13-month CCTA and at 45-day TEE **as well as clinical outcomes** will also be analyzed in the per-protocol and as-treated population.

Primary and secondary Analysis

Primary and secondary end points will be analysed on an intention-to-treat basis; as above mentioned some of them will be analysed also in the per-protocol and as-treated populations. Categorical outcome measures will be compared using a χ^2 test or Fisher exact test as required. Continuous variables will be compared using a 2-sided unpaired t test or a Mann-Whitney test, as appropriate. Estimation of the cumulative incidence of safety and efficacy endpoints will be performed using the Kaplan-Meier method, and event rates will be compared by the log rank test. The estimated relative risk (RR) is the ratio of the risk probabilities, and a confidence interval will be constructed based on a logarithmic transformation. Correlations between variables will be analyzed with a Cox regression.

Interim analyses

No statistical interim analyses planned.

Safety analysis

No statistical interim analyses planned.

Deviation(s) from the original statistical plan

Any deviation from the planned analyses will be reported in the final trial report.

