17.13 LAA PATENCY ASSESSED BY TEE

At 45 days after LAAC, patients will undergo a TEE assessment (and a CCTA as well). Device deployment will be assessed from 0° to 135° (0° - 45° - 90° - 135°) with and without color Doppler (using a scale 50-60 cm/sec). Presence of leak will be locally ascertained by expert echocardiographers with extensive previous and ongoing work imaging on LAAC devices. Leak on TEE is defined as any jet between LAA and LA or conversely detectable by means of color-Doppler (high velocity 50-60 cm/sec). The size is measured taking the narrowest flow region of the jet that occurs at, or just close to, the device.

Of note, rate of LAA patency at 45 day CCTA will be compared with rate of leak at 45 day TEE.

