4.1 Confidence intervals and *P* values

Primary and secondary end points will be analysed on an intention-to-treat basis. Additional analyses will be also carried out in the per-protocol and as-treated populations. Categorical outcome measures will be compared using a χ^2 test or Fisher exact test as required. Continuous variables will be compared using a 2-sided unpaired t test or a Mann-Whitney test, as appropriate. Estimation of the cumulative incidence of safety and efficacy end-points will be performed using the Kaplan-Meier method in case of time-to-event endpoints, and event rates will be compared by the log rank test. The estimated relative risk (RR) is the ratio of the risk probabilities, and a confidence interval will be constructed based on a logarithmic transformation.

The primary endpoint LAA patency or adjudicated cross-over including failed cross-over to other device at 45 days will be analyzed using risk ratios and risk differences.

All statistical tests will be performed using a 5% significance level.

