5.8 LAA assessments at 45 days of Follow-up

A Table of the LAA assessments (CCTA by the Core laboratory, TEE by the local teams) at 45-day visit will be produced, randomized to Amulet vs randomized to Watchman.

Table 5. Imaging assessment at 45 days visit

	Watchman/FLX N = xx	Amulet N = xx	Amulet vs Watchman Mean difference (95% p-value
CCTA assessment			
45day CCTA performed	n = xx, xx (%)	n = xx, xx (%)	x.x% (x.x%; x.x%)
Linear attenuation HU— mean (SD) ¶	n = xx, mean + sd	n = xx, mean + sd	x.XXX
Patent LAA — no. (%) ¶	n = xx, xx (%)	n = xx, xx (%)	x.XXX
LAA HU \geq 100 arterial phase — no. (%) ¶	n = xx, xx (%)	n = xx, xx (%)	x.XXX
LAA HU \geq 25% arterial phase — no. (%) ¶	n = xx, xx (%)	n = xx, xx (%)	x.XXX
Peridevice leak (PDL) — no. (%) ¶	n = xx, xx (%)	n = xx, xx (%)	x.XXX
Mixed leak (ML) — no. (%) ¶	n = xx, xx (%)	n = xx, xx (%)	x.XXX
Intradevice leak (IDL) — no. (%) ¶	n = xx, xx (%)	n = xx, xx (%)	x.XXX
Patent LAA with no visible leak — no. (%) ¶	n = xx, xx (%)	n = xx, xx (%)	x.XXX
Linear attenuation HU — mean venous phase (SD) ¥	n = xx, mean + sd	n = xx, mean + sd	n = xx, mean + sd
LAA patency venous phase — no. (%) ¥	n = xx, xx (%)	n = xx, xx (%)	x.XXX
LAA HU \geq 100 venous phase — no. (%) ¥	n = xx, xx (%)	n = xx, xx (%)	x.XXX
LAA HU on venous phase \geq 150% of LAA HU on arterial phase images — no. (%) ¥	n = xx, xx (%)	n = xx, xx (%)	x.XXX
Potential thrombus — no. (%)	n = xx, xx (%)	n = xx, xx (%)	x.XXX
Device related thrombus — no. (%)	n = xx, xx (%)	n = xx, xx (%)	x.XXX
TEE assessment			
45day TEE performed	n = xx, xx (%)	n = xx, xx (%)	x.XXX
Peridevice leak PDL — no. (%)	n = xx, xx (%)	n = xx, xx (%)	x.XXX
first PDL — no. (%)	n = xx, xx (%)	n = xx, xx (%)	x.XXX
PDL leak width — mm mean(SD)	n = xx, mean + sd	n = xx, mean + sd	n = xx, mean + sd
second PDL — no. (%)	n = xx, xx (%)	n = xx, xx (%)	x.XXX
PDL leak width — mm mean(SD)	n = xx, mean + sd	n = xx, mean + sd	n = xx, mean + sd
Any PDL width \geq 3mm — no. (%)	n = xx, xx (%)	n = xx, xx (%)	x.XXX
Device related thrombus — no. (%)	n = xx, xx (%)	n = xx, xx (%)	x.XXX

Data expressed as n (%), p-value from Fisher's tests) or means \pm standard deviations (p-value from unpaired t-tests) or median[IQR] (p-value from Mann-Whitney U-test).

CCTA: cardiac computer tomography angiography assessed by Core Laboratory. TEE: Transoesophagus Echocardiography assessed by local team.

Mixed PDL: PDL transferring into intradevice leak, or intradevice leak transferring into

[figure not shown]

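### The CCTA-versus-TEE comparison at 45 days is within patient, but the plan names only independent-group tests and no cross-tabulation or agreement measure for it.

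*Combined protocol and SAP*

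**What the plan says.** Protocol section 4.3 states that "a secondary objective of the study will be the comparison between TEE and CCTA with respect to LAA patency and device thrombus". Section 5.4 adds that "A comparison between CCTA and TEE at 45 days and then at 13 months will be performed" and gives validation of CCTA as the purpose. Section 9.2 specifies the contrast: "rate of LAA patency at 45 day CCTA will be compared with rate of leak at 45 day TEE". Section 17.13 repeats it and shows that the data are paired, since at 45 days "patients will undergo a TEE assessment (and a CCTA as well".

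The methods are in protocol section 12.4 and SAP section 4.1. Categorical outcomes get a chi-square "test or Fisher exact test as required". For the rest, "Continuous variables will be compared using a 2-sided unpaired t test or a Mann-Whitney test, as appropriate". Kaplan-Meier with log rank and a relative risk with a log-scale interval complete the SAP list; the protocol adds Cox regression. SAP section 6.2 adds Cox models, optional multiple imputation, a covariate for CCTA delay, and subgroups. SAP section 2.7 mentions comparing the two techniques but gives no method.

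The 45-day imaging output is SAP Table 5 (section 5.8): "CCTA by the Core laboratory, TEE by the local teams) at 45-day visit will be produced, randomized to Amulet vs randomized to Watchman". It has a CCTA block and a TEE block, each compared between arms.

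**The concern.** Each patient contributes one CCTA reading and one TEE reading, and the two should be positively correlated because they look for the same leak. A chi-square or Fisher test on the two marginal rates treats them as coming from different people. It ignores the covariance, so with positive correlation the interval is too wide and the p-value too large.

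The second problem matters more. Validating one modality against another needs to show how often they agree in the same patient. Two marginal rates carry no information on that, and no planned table shows the discordant patients. As written, the objective has no output that could answer it. This bears on the trial's rationale, because CCTA is the primary endpoint tool while the protocol background calls TEE the current gold standard.

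**Working it through.** **The plan's own figure.** The documents give no precision or power figure for the CCTA-TEE comparison. Their one such figure, power above 80% for 50% versus 30% with 100 per arm, reproduces at 82.8% (pooled normal formula, two-sided 5%). It concerns the between-arm primary endpoint and says nothing about the modalities.

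**Inputs (assumptions for this trial).** Protocol section 3.1 cites a series of 23 patients with both scans: 52% patent on CT, 34% on TEE, and 58% of the CT-patent also seen on TEE. The whole-number counts closest to this are 12 CT-positive, 8 TEE-positive and 7 positive on both. These counts are reconstructed; the protocol prints only percentages. The illustration takes n = 200, meaning that every planned patient has both scans assessable.

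**Standard error of the rate difference**

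- CT rate 12/23 = 0.522; TEE rate 8/23 = 0.348; difference 4/23 = 0.174.
- CT-only b = 5/23 = 0.217; TEE-only c = 1/23 = 0.043.
- Independent groups: √[(0.522×0.478 + 0.348×0.652)/200] = √(0.4764/200) = 0.0488.
- Paired: √[(b + c − (b − c)²)/200] = √[(0.2609 − 0.0302)/200] = 0.0340.
- Ratio 0.0488/0.0340 = 1.44. It does not depend on n. Half-widths (×1.96) are 9.6 and 6.7 percentage points.

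The printed percentages used directly (both positive = 0.58 × 0.52 = 0.302) give 0.0487 and 0.0335, a ratio of 1.45.

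**Range over overlap, n = 200**

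| CT / TEE rates | Both positive | Independent SE | Paired SE | Ratio |
|---|---|---|---|---|
| 52% / 34% | 0.177 (independence) | 0.0487 | 0.0487 | 1.00 |
| 52% / 34% | 0.260 | 0.0487 | 0.0392 | 1.24 |
| 52% / 34% | 0.340 (full nesting) | 0.0487 | 0.0272 | 1.79 |
| 62% / 36% | 0.223 (independence) | 0.0483 | 0.0483 | 1.00 |
| 62% / 36% | 0.360 (full nesting) | 0.0483 | 0.0310 | 1.56 |

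The 62% / 36% pair is from the second series cited in section 3.1 (19 patients), for which no overlap is given. The range covers zero to positive association. Less overlap than chance would reverse the direction, but that is implausible for two tests of the same leak.

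**Effect on the test.** With equal true rates and correlation φ, the actual size of a nominal 5% independent test is 2 × [1 − Φ(1.96/√(1 − φ))]: 2.8% at φ = 0.2, 1.1% at 0.4, 0.6% at 0.5. At the cited rates and overlap (φ about 0.53), power with 160 to 200 pairs is at least 97% with either method.

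**Why marginal rates cannot show agreement.** Take 200 patients with 104 CT-positive and 68 TEE-positive. Chance agreement is 0.52×0.34 + 0.48×0.66 = 0.494.

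- All 68 TEE-positives also CT-positive: observed agreement (68 + 96)/200 = 0.82; kappa = (0.82 − 0.494)/(1 − 0.494) = 0.64.
- Only 36 positive on both: observed agreement (36 + 64)/200 = 0.50; kappa = (0.50 − 0.4936)/(1 − 0.4936) = 0.01.

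The two marginal rates are identical in both cases.

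**The case against.** The strongest reply is that the method is unspecified rather than wrong. SAP section 6.1 scopes outcome comparisons to Amulet versus Watchman, Table 5 is laid out that way, and for those contrasts independent-group tests are correct. A reader might infer that the plan prescribes a chi-square or Fisher test for CCTA against TEE; the documents do not say so. This stands. The standard-error result is conditional on applying the general rule, and what is certain is the absence of any paired or agreement method.

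A reader might also infer that the comparison has two competing TEE definitions, because protocol section 5.1 and SAP section 1.2 use residual flow of at least 3 mm. That does not hold. The comparison is with TEE *leak*, which protocol sections 9.2 and 17.13 both define as any colour-Doppler jet. The 3 mm criterion is attached to TEE *patency*, and Table 5 reports both.

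The error is conservative and, at the cited rates, would not change a test's conclusion. That stands too, but it does not supply an agreement analysis.

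The objective's standing is also uneven: secondary in section 4.3, filed under other outcomes in section 5.4, and absent from the secondary outcome lists. That lowers the priority, but the objective still needs an analysis.

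**Conclusion.** The point holds as a gap in the analysis plan for a stated secondary objective. The data are paired, every categorical test named assumes independent groups, and no planned table crosses CCTA with TEE. Under the general rule the standard error would be about 1.44 times the paired one, on rates reconstructed from one small series, with a range of 1.00 to 1.79 from independence to full nesting. The direction is conservative under positive correlation. The more serious loss is that the validation purpose cannot be met from marginal rates.

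Nothing here touches the primary endpoint or any other between-arm comparison, and no data would be lost, since both readings are collected per patient. The change should be made, but the trial's main conclusion does not depend on it.

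**What to change.** Add one paragraph to SAP section 6.2.2 and one small table.

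- **LAA patency, 45 days.** In patients with both scans assessable, give a 2x2 table of CCTA patency by TEE leak, overall and by arm. Report the paired risk difference with 95% CI, McNemar's test, positive and negative agreement, and kappa. Use any jet as TEE leak, as protocol sections 9.2 and 17.13 already define it, with at least 3 mm as a sensitivity analysis.
- **Device thrombus, 45 days.** Do the same, but first state how a CCTA reading of *possible* is classified. Protocol section 17.11 scores CCTA thrombus as positive, possible or negative, and Table 5 has a separate row for potential thrombus, so a 2x2 table needs this rule. Use the other classification as a sensitivity analysis.
- **13 months.** Label any comparison descriptive. Under protocol section 9.1.4, TEE is then done only if clinically indicated, so the pairs are a selected subset.

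No new data, visits or scans are needed.

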10. CARDIAC COMPUTER TOMOGRAPHY ANGIOGRAPHY

10.1 CCTA PROTOCOL¹⁹

The CCTAs will be carried out according an identical protocol, by using a 64- to 320-detector scanner, with a multiphasic acquisition. Iodinated contrast medium (70–90 mL) will be administered through an antecubital vein (flow rate: 5 mL/s), followed by 50 mL of saline chaser bolus (sodium chloride 0.9%), administered at the same flow rate. Patients will receive nitroglycerin, if no contraindicated (known sensitivity to nitrate medications, administration of PDE5 inhibitor medications within the past 24 hours, systolic blood pressure <90 mmHg, history of increased intracranial pressure, severe anemia), and betablockers (aimed at achieving a heart rate of <65 beat/min) prior to the CCTA acquisition. A prospective high-pitch flash mode or broad coverage single shot/step and shoot ECG-gated CT acquisition technique typically at 70 % of R–R interval or a retrospectively ECG gated CT-acquisition at 30–70 % of R–R interval will be used. The dose modulation will be used when possibleExposure parameters will be adjusted according to patient size. Images will be reconstructed using iterative reconstruction or filtered back-projection at 0.75 mm slice width, 0.5 mm slice increment. The standard scan will be performed using a bolus tracking technique for optimal scan acquisition timing. The delayed scan will be performed 60 s following the beginning of the standard scan to allow contrast equilibration within the blood pool. The delayed scan will be planned at the level of the carina and extended 4–8 cm caudally to include the LAA but not the whole heart, to minimize unnecessary radiation exposure.

10.2 Adjunctive CCTA analyses

Adjunctive analyses not included among study endpoints, will be performed.

10.2.1 Further LAA patency analyses

In the event of LAA patency, two elements will be assessed: presence of PDL, presence of intradevice leak. PDL, defined as a visible continuity of contrast between LA and LAA along the side of the device, will be looked for on the lobe margins (and on the disk margins in Amulet patients as well) by using reconstructed plane parallel to LAA orifice.

Intradevice leak, defined as a visible continuity of contrast through the entire length of the device, will be looked for by using reconstructed plane parallel to device long axis. In the event that an intradevice leak is incomplete, passing only through a portion of the device and then continuing at its margin (or vice versa), the leak will be defined as "mixed".

The device covering will be semiquantitatively evaluated on venous phase and scored by the ICL as one of the following: device completely uncovered, device covered less than 50%, device covered more than 50%, device completely covered.

10.2.2 Adjunctive CCTA criteria for LAA closure

In order to evaluate the complete LAA occlusion with the CCTA, we proposed following criteria

Amulet-CT criteria for LAA occlusion	Watchman/FLX -CT criteria for LAA occlusion
Lobe compression >10%	Position: plane of maximum diameter of the device is at or just distal (<2 mm) to the orifice of the LAA, and that it spans the entire LAA ostium. Position of the lobe in relation to left lateral ridge
Disc-lobe separation (>2 mm)	Size: measure the plane of the maximum diameter of the device, ensuring the threaded insert is visible. The device should be 80-92% of the original size
Device axis consistent with landing zone and landing zone and angle between disc and lobe	Seal: no contrast in the distal lobes
Concave disc	Consistency between device axis and ostium
Width of the lobe is $\geq 2/3$ within the circumflex artery and position of the disc in relation to left lateral ridge	Lobe's shape
Lobe's shape	

Lobe compression (%) was calculated as: $[(\text{manufacturer device diameter} - \text{measured diameter})/\text{manufacturer device diameter}] \times 100\%$

10.2.3 Amulet subgroup

Due to the double system of closure in Amulet device, some additional data will be collected in this subgroup. The HU will be measured, if possible, also in the small region between the disc and the lobe by the same method used to assess LAA patency.

Furthermore, in addition to PDLs assessment, that in Amulet subgroup refer to the leak passing along the side of the lobe, leaks passing marginally to the disc (peridisc leaks) will be assessed as well (with the same method used for PDLs). Finally, in Amulet subgroup the percentage of disc covering will be assessed as well.

